- Crude prevalence of the major congenital malformations will be reported according to first-trimester exposure to pregabalin and the comparators. Crude prevalence of the other birth outcomes will be reported according to any trimester exposure to pregabalin and the comparators (unexposed, lamotrigine, duloxetine and lamotrigine or duloxetine. Lamotrigine and duloxetine chosen because they have indications similar to that of pregabalin [lamotrigine (epilepsy), duloxetine (GAD, neuropathic pain)]).
- Crude and propensity-score adjusted prevalence ratios will be estimated for the birth outcomes comparing pregnancies exposed to pregabalin during first trimester versus the four comparators.
 - Analyses will be conducted for all pregabalin exposed pregnancies, overall (i.e. all first trimester pregnancies irrespective of indication of use). Pregnancies ending in singleton/multiple live birth, stillbirth will be used.
 - Separate analyses will be conducted for pregabalin monotherapy.

Secondary analyses:

Will be similar to the primary analyses but with pre-specified postnatal neurodevelopmental outcomes.

Sensitivity analyses:

The analyses of major congenital malformations will be repeated with the inclusion of pregnancies ending in 2nd trimester therapeutic induced abortions (in all countries except Sweden).

Meta-analyses:

Country-specific crude and adjusted estimates of association will be combined in a meta-analysis.

Milestones: Pfizer will initiate the study upon endorsement of the protocol by the EMA. The earliest estimated timeline to submit the study report to the EMA is in the fourth quarter of 2019) (Q4 2019).

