7. RESEARCH QUESTION AND OBJECTIVES

The study objectives are to describe the use of pregabalin exposure in pregnancy and to estimate the risk of major congenital malformations, birth outcomes other than congenital malformations and neurodevelopmental outcomes with the use of pregabalin. Association between pregabalin exposure and a given safety outcome will be assessed for pregabalin exposure during a relevant gestational period using, alternatively, unexposed subjects and subjects exposed to treatments with indications similar to those of pregabalin (active comparators); effect exposure to pregabalin monotherapy will be assessed in a sensitivity analysis.

The specific primary objectives of the study are to:

- Describe use of pregabalin, lamotrigine, and duloxetine during pregnancy overall, by trimester and by calendar year of delivery in pregnancies ending in live or stillbirths, as characterized by
 - Prevalence of use (proportion of pregnancies with 1 or more dispensing of a given drug),
 - Distribution of therapeutic indications among the exposed pregnancies (epilepsy, GAD, neuropathic pain),
 - Cumulative dose, based on dispensings count and amount dispensed in each;
- Describe the prevalence of (proportion of live or stillborn children with) major congenital malformations after first-trimester in-utero exposure to pregabalin (yes/no); after first-trimester exposure to lamotrigine, after first-trimester exposure to duloxetine, after first-trimester exposure to lamotrigine or duloxetine, in pregnancies ending in live or still birth; in live or stillborn children unexposed to antiepileptics in the first trimester; and in the total population of live or stillborn children;
- Estimate the association between first-trimester exposure to pregabalin and prevalence of major congenital malformations, as compared with no first-trimester exposure to pregabalin, with first-trimester exposure to lamotrigine, with first-trimester exposure to duloxetine, and first-trimester exposure to lamotrigine or duloxetine, in live or stillborn children;
- Describe the prevalence of birth outcomes other than major congenital malformations (listed in [Section 8.3.2.1](#)) according to exposure (yes/no) to pregabalin any time

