8.3. Variables

8.3.1. Exposures

For the purposes of timing of exposure, trimesters of pregnancy will be defined as follows:

- First trimester: from the first day of the last menstrual period (LMP)-90 days to LMP+97 days (both dates inclusive);
- Second trimester: from LMP+98 days to LMP+202 days (both dates inclusive);
- Third trimester: from LMP+203 days (inclusive) until pregnancy end date (not included).

Exposure during the first trimester

Pregabalin exposure during the first trimester will be defined as at least one maternal dispensing of pregabalin during the first trimester. Pregabalin monotherapy in the first trimester will be defined as first-trimester exposure to pregabalin and no first-trimester dispensing for any other AED.

Comparators:

Unexposed to pregabalin during the first trimester comparator is defined as pregnancies without a dispensing for pregabalin or any other AED, including lamotrigine or duloxetine, during the first trimester.

Lamotrigine exposure in the first trimester is defined by at least one dispensing of lamotrigine during the first trimester. Lamotrigine monotherapy in the first trimester will be defined as first-trimester exposure to lamotrigine and no first-trimester dispensing for any other AED.

Duloxetine exposure in the first trimester is defined by at least one dispensing of duloxetine during the first trimester. Duloxetine monotherapy in the first trimester will be defined as first-trimester exposure to duloxetine and no first-trimester dispensing for any AED.

Lamotrigine or duloxetine exposure in the first trimester is defined by at least one dispensing of lamotrigine or duloxetine or both during the first trimester. Lamotrigine or duloxetine monotherapy in the first trimester will be defined as first-trimester dispensing of lamotrigine or duloxetine or both and no first-trimester dispensing for any other AED.

For analyses that use lamotrigine as the comparator, pregnancies exposed to both pregabalin and lamotrigine in the first trimester will be excluded. For analyses that use duloxetine as the comparator, pregnancies exposed to both pregabalin and duloxetine in the first trimester will be excluded.

Exposure any time during pregnancy

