Pregabalin exposure any time during pregnancy is defined by at least one dispensing of pregabalin during any trimester. Pregabalin monotherapy any time during pregnancy will be defined as any-pregnancy exposure to pregabalin and no dispensing for any other AED during any trimester.

Comparators:

Unexposed to pregabalin during any trimester comparator is defined as pregnancies without dispensing for pregabalin or other AEDs including lamotrigine, or duloxetine during any trimester.

Lamotrigine exposure any time during pregnancy is defined by at least one dispensing of lamotrigine during any trimester. Lamotrigine monotherapy any time during pregnancy will be defined as any-pregnancy exposure to lamotrigine and no dispensing for any other AED during any trimester.

Duloxetine exposure any time during pregnancy is defined by at least one dispensing of duloxetine during any trimester. Duloxetine monotherapy any time during pregnancy will be defined as any-pregnancy exposure to duloxetine and no dispensing for any AED during any trimester.

Lamotrigine or duloxetine exposure any time during pregnancy defined by at least one dispensing of lamotrigine or duloxetine or both during any trimester. Lamotrigine or duloxetine monotherapy any time during pregnancy will be defined as any-pregnancy exposure to lamotrigine or duloxetine or both and no dispensing for any other AED during any trimester.

For analyses that use lamotrigine as the comparator pregnancies exposed to both pregabalin and lamotrigine in any trimester will be excluded. For analyses that use duloxetine as the comparator pregnancies exposed to both pregabalin and duloxetine in any trimester will be excluded.

In a sensitivity analysis, monotherapy with pregabalin, lamotrigine, and/or duloxetine will be defined by absence of other AED, selective serotonin reuptake inhibitors, or benzodiazepines.

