8.3.3. Covariates and other population characteristic

Characteristics of the study population will include perinatal covariates and covariates of the mother. Perinatal covariates include calendar year of delivery, maternal age at conception, parity (number of live and still births prior to the on-study pregnancy); marital/cohabiting status; pregravid body mass index (BMI) as recorded at the first antenatal visit or via a hospital diagnosis of obesity; smoking during pregnancy as recorded at the first antenatal visit; single or multiple gestation; Caesarean delivery; and child's sex. Caesarean delivery and child's sex will be reported but will not be used for adjustment. Indication for pregabalin use in 12-months pre-LMP (epilepsy, neuropathic pain, GAD and related disorders) will be reported descriptively but will not be used for adjustment.

[figure not shown]
Covariates of the mother considered for adjustment (inclusion in propensity-score model) will include:

- calendar year of delivery;
- age in years at conception;
- marital/cohabiting status;
- smoking during pregnancy;
- Obesity (BMI ≥ 30 kg/m²) or a hospital diagnosis of obesity;
- Single or multiple gestation
- hospital-recorded morbidity based on inpatient and outpatient specialist care or proxy medication use in 12 months pre-LMP: migraine or other headache syndromes, other neurologic disorders, depression, bipolar disorder, alcohol abuse or dependence, drug abuse or dependence, hypertension, haematological diseases, diabetes, asthma, liver diseases, renal impairment, rheumatic diseases, obesity, disorders of female pelvic organs/genital tract, thyroid disorders, infections [infections will be assessed in 90 days pre-LMP]. In Finland, in addition to the hospital diagnoses, diagnoses from primary care are also available and will be used;
- indicators of maternal health care utilisation in the 12 months pre-LMP (number of inpatient and specialised outpatient encounters);
- for the outcome congenital malformations: maternal medication use each as a dichotomous variable, defined by at least one dispensing during the first trimester (AEDs, antidepressants, hypnotics, antipsychotics, analgesics, antihypertensives, non-steroidal anti-inflammatory drugs, drugs for peptic ulcer/gastroesophageal reflux, folic acid, drugs for in-vitro fertilization, thyroid hormones, systemic corticosteroids, and antiinfectives for systemic use);

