8.7.3.1. Computation of propensity scores

To account for confounding by the measured covariates, adjusted analysis will be conducted using propensity score (PS) stratification, following the approach by Paterno et al.⁴ For each pregnancy, a PS will be computed, using logistic regression, as the probability being exposed to pregabalin vs. given comparator conditional on the measured covariates listed in [Section 8.3.3](#) and [Annex 3](#).⁵³

PS will be estimated for each pregnancy using a generic-outcome model, meaning that all prespecified covariates will be included in the PS-estimating model, regardless of the outcome. Wyss et al showed, in a simulation study, that such model performs well when multiple outcomes are being examined;⁵⁴ furthermore, it is reasonable to assume in this study that all confounders distort the association in the same direction for all outcomes. In case of model non-convergence, covariates with the smallest cell counts (corresponding to the lowest prevalence of covariates) will be removed one-by-one until convergence is achieved.

A separate PS will be estimated for each study population and contrast. To summarise, the following sets of propensity scores will be estimated:

1. First-trimester pregabalin vs. first-trimester unexposed
2. First-trimester pregabalin vs. first-trimester lamotrigine
3. First-trimester pregabalin vs. first-trimester duloxetine
4. First-trimester pregabalin vs. first-trimester duloxetine or lamotrigine
5. First trimester pregabalin monotherapy vs. first-trimester unexposed
6. First trimester pregabalin monotherapy vs. first-trimester lamotrigine monotherapy
7. First trimester pregabalin monotherapy vs. first-trimester duloxetine monotherapy
8. First-trimester pregabalin monotherapy vs. first-trimester duloxetine or lamotrigine monotherapy
9. Any-trimester pregabalin vs. any-trimester unexposed
10. Any-trimester pregabalin vs. any-trimester lamotrigine
11. Any-trimester pregabalin vs. any-trimester duloxetine
12. Any-trimester pregabalin vs. any-trimester duloxetine or lamotrigine
13. Any-trimester pregabalin monotherapy vs. unexposed
14. Any-trimester pregabalin monotherapy vs. any-trimester lamotrigine monotherapy
15. Any-trimester pregabalin monotherapy vs. any-trimester duloxetine monotherapy
16. Any-trimester pregabalin monotherapy vs. any-trimester duloxetine or lamotrigine monotherapy

After estimation of each PS, the following steps will be taken in each country:

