- a graph showing distribution of PS of the exposed and unexposed pregnancies will be produced and pregnancies with PS in non-overlapping areas will be deleted (trimming).
- based on the trimmed distributions, strata of PS will be defined using boundaries of the pregabalin-exposed pregnancies. Number of strata will be determined by the number of exposed pregnancies and will vary across countries.
- all exposed and unexposed pregnancies included in a given PS estimation will be classified into these strata based on their PS.
- A weight will be assigned to each unexposed pregnancy based on its stratum; each exposed pregnancy will assigned the weight of 1.
- A weighted regression analysis will be performed, in which adjusted prevalence ratios or adjusted hazards ratios are estimated using a weighted regression model.

Balance of the covariates following trimming and stratifications-strata specific weights will be assessed in each country's dataset using standardised mean differences. Covariates with standardised mean differences <0.1 will be considered balanced. Initially only first-order variables will be entered into the PS models; if imbalance persists, use of interaction terms will be considered. PS will be estimated by an analyst in each country and the final PS models that achieve acceptable covariate balance may be different in each country.

The crude and the adjusted country-specific estimates of association will be reported separately and combined in a meta-analysis (described in [Section 8.7.7](#)).

If feasible, prevalence ratios will be estimated among women with >1 pregnancies discordant with respect to pregabalin exposure in country-specific analyses only (not in meta-analyses).

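### In the adjusted pregabalin-versus-unexposed contrasts (1 and 9), the propensity score includes AED use, which the comparator definition fixes at zero, so polytherapy pregnancies are either trimmed away or left unadjusted for co-AED use

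*Protocol*

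**What the plan says.** **Exposed group.** Section 8.3.1: "Pregabalin exposure during the first trimester will be defined as at least one maternal dispensing of pregabalin during the first trimester". Other AEDs are allowed. Monotherapy (no other AED) is a separate definition with its own contrasts, 5 and 13 in the numbered list of Section 8.7.3.1. The Abstract says of the main analysis: "Analyses will be conducted for all pregabalin exposed pregnancies, overall".

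**Unexposed comparator.** For first-trimester exposure: "Unexposed to pregabalin during the first trimester comparator is defined as pregnancies without a dispensing for pregabalin or any other AED". For exposure at any time: "Unexposed to pregabalin during any trimester comparator is defined as pregnancies without dispensing for pregabalin or other AEDs including lamotrigine, or duloxetine".

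**Covariates.** Section 8.3.3 includes maternal medication use, "defined by at least one dispensing during the first trimester (AEDs, antidepressants, hypnotics" and further classes. For outcomes other than malformations the same list applies to any trimester.

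**PS model and trimming.** Section 8.7.3.1 enters all prespecified covariates whatever the outcome and exempts no contrast. If the model does not converge, "covariates with the smallest cell counts (corresponding to the lowest prevalence of covariates) will be removed one-by-one until convergence is achieved". After estimation, "pregnancies with PS in non-overlapping areas will be deleted (trimming". A standardised mean difference (SMD) below 0.1 counts as balanced, and final models may differ between countries. Section 8.7.7 then pools the country estimates by fixed effects.

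**Objectives.** For malformations, Section 7 states the reference as "as compared with no first-trimester exposure to pregabalin". For the other birth outcomes it lists absence of pregabalin and absence of antiepileptics as two separate references. Section 8.3.1 defines only the AED-free one.

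**The concern.** A PS can balance a covariate only if each of its values can occur in both groups. In contrasts 1 and 9, AED use is zero for every comparator by definition but varies among the exposed. The protocol then gives two mechanical rules, trimming and removal of the rarest covariate, that resolve the conflict in opposite ways. It does not say which should apply.

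The distinction at stake is one the study is meant to inform. Section 6 reports combined earlier evidence as an adjusted risk ratio of 1.3 for any first-trimester pregabalin and 1.0 for monotherapy. If the adjusted overall contrast quietly turns into the monotherapy contrast, the report presents one quantity under the label of the other. The crude estimate would still include polytherapy, so the crude-to-adjusted change would mix confounding with a change of population. If the covariate is dropped instead, the overall estimate carries any effect of co-administered AEDs.

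**Working it through.** **1. The plan's own figure.** Section 8.5 and Table 5 assume 1,000 exposed, a 119:1 ratio, 3% prevalence, a true risk ratio of 1, a 95% interval and 80% probability.

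Upper limit = exp[(z0.975 + z0.80) × SE], with SE = √[(1−p)/(n₁p) + (1−p)/(n₀p)].

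SE = √[0.97/30 + 0.97/3,570] = √0.03261 = 0.1806. Limit = exp(2.8016 × 0.1806) = 1.658. The protocol gives 1.65845, so the figure is reproduced.

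**2. The structure.** Let A = 1 if another AED was dispensed in the window.
- Comparator: A = 0 for all.
- Exposed: A = 1 for a share q, which the protocol does not give.
- Every pregnancy with A = 1 is exposed, so the logistic likelihood rises without bound in the coefficient of A and no finite maximum exists. This is quasi-complete separation.

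**3. Branch one: A stays in the model.** The PS step was simulated with 1,000 exposed, 119,000 unexposed and assumed distributions for age, smoking, depression, analgesics and hypnotics. Pregnancies outside the common PS range were deleted.
- q = 5%, 20% and 40%, two runs each: the coefficient of A ran to 27.9–31.7, polytherapy PS was about 1.0, and no polytherapy pregnancy was kept.
- 200 exposed, q = 20%: 0 of 42 polytherapy pregnancies kept.
- Across all runs the highest PS in the unexposed was 0.71–0.94, and 97–100% of monotherapy pregnancies were kept.
- Iteration limit: the routine reported convergence at limits of 25 and 100, but not at 5, 8 or 12. Polytherapy fell outside the overlap in all of these runs.

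The trimmed exposed set is therefore in effect the monotherapy set, and contrasts 1 and 9 become contrasts 5 and 13. Afterwards A is zero in both groups, so the SMD check raises no alarm.

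**4. Branch two: non-convergence is declared.** The PS is fitted by country. With Table 4 counts and an assumed q of 20%, A = 1 in 0.20 × 200 = 40 of 730,000 Danish pregnancies (0.005%) and 0.20 × 700 = 140 of 580,000 Finnish ones (0.024%). Prevalences of the other covariates are not given, but at this rarity A would probably go early. With A removed, the simulation kept 183 of 184 (q = 20%) and 385 of 392 (q = 40%) polytherapy pregnancies. They are then compared with AED-free women. The imbalance is SMD = q/√[q(1−q)/2]. Neither weighting nor interaction terms can reduce it, because no comparator has A = 1.

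**5. Size by assumed share.** The limit applies to branch one at 3% prevalence, with the unexposed fixed at 119,000. The SMD applies to branch two, against the plan's threshold of 0.1.

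| q (assumed) | exposed left if trimmed | upper limit | SMD of A if kept |
|---|---|---|---|
| 0 | 1,000 | 1.66 | – |
| 5% | 950 | 1.68 | 0.32 |
| 10% | 900 | 1.70 | 0.47 |
| 20% | 800 | 1.76 | 0.71 |
| 40% | 600 | 1.92 | 1.15 |

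**The case against.** **The covariate list is only under consideration.** Section 8.3.3 does speak of covariates considered for adjustment. Section 8.7.3.1 then takes that discretion away by entering all of them.

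**The diagnostics would show it.** PS graphs and SMDs are required in each country, so an analyst would probably see a cluster of exposed pregnancies near PS = 1. That stands. But the prescribed response to non-overlap is deletion, the balance check afterwards looks clean, and the text does not require the number of deleted polytherapy pregnancies to be reported.

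**The reference group is deliberate.** The AED-free and duloxetine-free comparator is defined the same way in the Abstract and in Section 8.3.1. That stands too: nothing here shows the comparator must be replaced, and the looser wording in Section 7 calls for alignment.

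**Precision suffers little and other analyses are untouched.** This is correct for modest polytherapy shares. Crude estimates are unaffected, and contrasts 5 and 13 are already restricted to pregnancies without other AEDs.

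**Stronger readings.** A reader might infer that every polytherapy pregnancy is certain to be trimmed. The text does not support that, because the non-convergence rule can remove the covariate first, and the outcome depends on software and iteration limit. A reader might also infer that all exposed pregnancies are lost because the AED covariate counts pregabalin itself, or that the duloxetine contrasts fail in the same way because antidepressants count duloxetine. Both depend on the Annex 3 code lists, which are not shown. The reference to pregabalin and any other AED in Section 8.3.1 neither settles the coding nor excludes that reading.

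**Conclusion.** The concern holds for the adjusted contrasts 1 and 9. The comparator definition and the PS specification cannot both be applied as written without a positivity failure. Either polytherapy is trimmed and the overall estimate is in effect the monotherapy one, or AED use is dropped and co-AED use goes unadjusted. The branch may differ by country, and the fixed-effects meta-analysis could then pool different populations. That countries will actually diverge is a possibility the text allows, not something it shows.

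The separation itself follows from the definitions and needs no assumed figure beyond some co-AED use among the exposed. The size does need one: q is not in the protocol, and the simulated covariates are invented, although zero retention of polytherapy on branch one did not depend on q. The loss of precision is modest at low shares. The main damage is to the meaning of the overall adjusted estimate in the comparison that Section 6 calls primary.

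**What to change.** 1. Define the AED covariate as AEDs other than pregabalin.
2. In contrasts 1 and 9, omit it from the PS model in all four countries, giving as the reason that it is structurally zero in the comparator. Show it in the balance table as a known structural difference.
3. State that contrasts 1 and 9 estimate pregabalin with or without other AEDs versus no AED or duloxetine, and that contrasts 5 and 13 give the estimate free of co-administered AEDs.
4. Amend the non-convergence rule so that covariates structurally constant in one group are removed before the rarest-covariate rule applies.
5. Report, by country and contrast, how many polytherapy pregnancies were trimmed.
6. Align the references to no pregabalin exposure in Section 7 with the comparator in Section 8.3.1.

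If the sponsor also wants a reference group unexposed to pregabalin only, it can be an additional analysis. The AED and antidepressant covariates there must include lamotrigine and duloxetine, or co-use of those drugs would be present in both groups without being balanced.

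The cost is protocol wording and a change to the covariate code, with no new data. The small downside is that the overall contrast is openly not adjusted for co-AED use.
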